#### **9.1.3. Treatment Phase (Partially-Blind)**

Assessments to be performed during the treatment phase are specified in the [TIME AND EVENTS SCHEDULE](#).

Eligible subjects will be randomized on Day 1. Study drug should be taken in the morning at approximately the same time each day, together with breakfast, except for ETV which should be taken on an empty stomach.

#### **9.1.4. Treatment Extension Phase (Partially-Blind)**

For subjects who participate in the treatment extension phase, treatment will be continued without interruptions. Study drugs should be taken in the morning at approximately the same time each day with breakfast, except for ETV which should be taken on an empty stomach.

Assessments to be performed during the treatment extension phase are specified in the [TIME AND EVENTS SCHEDULE](#).

At the Week 20 visit and the Week 24 visit, eligibility to participate in the treatment extension phase will be checked. The procedures are specified in the [TIME AND EVENTS SCHEDULE](#).

#### **9.1.5. Post-Treatment Phase (Follow-Up)**

For details on the follow-up after the last study drug intake of the study treatment phase (Week 24 or Week 48) or in case of dropout, please refer to the [TIME AND EVENTS SCHEDULE](#) for the post-treatment (follow-up) phase. All subjects who received 24 weeks of treatment, who received 48 weeks of treatment and did not meet the treatment completion criteria as described in Section 6.3, or who discontinued study treatment early (either 24 or 48 weeks of study treatment) will be followed-up for 24 weeks (Schedule 1). Subjects who meet the study completion criteria (see Section 6.3) will be followed-up for 48 weeks (Schedule 2).

If a subject withdraws from the study (ie, withdrawal of consent), the subject will be offered an optional safety follow-up visit.

### **9.2. Efficacy Evaluations**

Efficacy assessments will be performed at the time points indicated in the [TIME AND EVENTS SCHEDULE](#).

Qualitative and quantitative HBsAg and HBeAg, and quantitative HBcrAg as well as anti-HBs and anti-HBe antibodies will be determined using standard serologic assays in a central laboratory. Samples for the determination of HBsAg and HBeAg will be processed in real-time using an assay such as the ARCHITECT platform (Abbott Laboratories). Samples for the determination of HBcrAg can be analyzed in batch and at the sponsor's discretion.

HBV DNA and HBV RNA will be quantified at a central laboratory using in vitro nucleic acid amplification tests for the quantification of HBV DNA and HBV RNA. Samples for the determination of HBV DNA will be processed in real-time using a test such as the COBAS® TaqMan® HBV Test, v2.0 (Roche Molecular Systems). Samples for the determination of HBV RNA can be analyzed in batch and at the sponsor's discretion.

Post-baseline results from HBsAg, HBeAg, anti-HBs, and anti-HBe antibody testing will be provided to the investigator and the sponsor from Week 20 onwards. HBV DNA results will be provided to the investigator and the sponsor from screening until FU Week 24 or 48, as applicable. It is the responsibility of the investigator:

- To monitor HBV DNA results and ensure that JNJ-56136379 treatment is discontinued in subjects with viral breakthrough and in treatment-naïve subjects with  $<1 \log_{10}$  IU/mL decline in HBV DNA from baseline at Week 4 and Week 8 (see Section 10.2)
- To monitor HBV DNA to assess if treatment extension criteria (see Section 6.1) are met
- To assess if treatment completion criteria (see Section 6.3) are met
- To assess whether re-start of NA treatment during follow-up is needed (see Section 6.4).

In subjects from the pharmacokinetic subgroup and subjects enrolled at a site with an on-site Fibroscan device, Fibroscan assessments will be performed to determine changes in fibrosis.

The blinded data collected from baseline onwards will be provided to the investigator at the end of the study to complete the subject's medical records.

Samples may be used by the sponsor for additional exploratory assessments analyzing the serologic and virologic characteristics of HBV infection and efficacy or safety of the study treatment.

### **9.3. Sequencing**

Viral genome sequence analysis will be performed to identify pre-existing baseline polymorphisms and to evaluate emergence of mutations associated with JNJ-56136379 and/or ETV or TDF treatment.

Sequencing of the HBV genome will be performed to monitor HBV variants present at the time points indicated in the **TIME AND EVENTS SCHEDULE**. Samples at baseline will be sequenced by default if HBV DNA levels are within the ranges required for the sequencing assay. The sequencing of samples after baseline may be triggered by the sponsor virologist based

on changes in HBV DNA levels observed in each individual subject and the limits of the sequencing assay.

Samples may be used by the sponsor for additional assessments analyzing the serologic and virologic characteristics of the HBV infection and efficacy of the study treatment, including viral genotypic and phenotypic assessments.

## **9.4. Pharmacokinetics**

### **9.4.1. Evaluations**

Venous blood samples will be collected for the determination of plasma concentrations of total JNJ-56136379 and/or NA (ETV or TDF), as applicable, at time points specified in the **TIME AND EVENTS SCHEDULE**.

24-hour urine sampling will be performed in approximately 35% of all subjects (pharmacokinetic subgroup, at selected sites only) for the determination of JNJ-56136379 or NA (ETV or TDF) concentrations, as applicable, on Day 1 and Day 84 (Week 12) (0-2, 2-12, and 12-24 hours postdose). This 24-hour sampling schedule will require an overnight stay on site.

Based on the individual plasma concentration-time data, using the actual dose taken and the actual sampling times, pharmacokinetic parameters and exposure information of JNJ-56136379 will be derived using popPK modeling. Data may be combined with those of a selection of Phase 1 studies to support a relevant structural model. Available subject characteristics (eg, demographics, laboratory variables, genotypes) will be tested as potential covariates affecting pharmacokinetic parameters.

Plasma samples will also be collected from female subjects using hormonal contraceptives that can be analyzed further for determination of plasma concentrations of hormonal contraceptives and their metabolites. These samples will be analyzed at the sponsor's discretion. The start of contraceptive administration at the last initiated cycle (if applicable for the type of contraception) will be documented in the eCRF.

### **9.4.2. Analytical Procedures**

A selection of plasma samples will be analyzed to determine concentrations of total JNJ-56136379 and NA (ETV or TDF) using a validated liquid chromatography-mass spectrometry (LC-MS/MS) method by or under the supervision of the sponsor. A selection of urine samples will be analyzed to determine JNJ-56136379 and NA (ETV or TDF) concentrations using a qualified LC-MS/MS method. In addition, plasma samples may be analyzed for hormonal contraceptives and important metabolites, at the sponsor's discretion.

At the sponsor's discretion, plasma and urine samples may be analyzed for metabolite profiling using a qualified method. In addition, plasma and urine pharmacokinetic samples may be stored for future exploratory analysis of protein binding or the metabolite profile.

To allow selection of samples, the bioanalytical laboratory will receive randomization lists per planned interim analysis and/or upon request of the bioanalytical scientist. Unblinding of the treatment code will be performed at the bioanalytical laboratory only, and will be subjected to a procedure that will ensure that codes will not be revealed to anyone involved in the execution of the study. Note that blinding does not apply to the JNJ-56136379 monotherapy arms.

### **9.4.3. Pharmacokinetic Parameters**

#### **9.4.3.1. Pharmacokinetic Analysis on Plasma Samples**

Based on the individual plasma concentration-time data, using the actual sampling times (see **TIME AND EVENTS SCHEDULE**), the following pharmacokinetic parameters will be derived for JNJ-56136379 and/or NA (ETV or TDF) as applicable:

- On Day 1:  $t_{max}$ ,  $C_{max}$ ,  $C_\tau$ ,  $AUC_\tau$ ,  $CL/F$
- At Weeks 1, 2, 4, 8, 20, 24, 28, 32, 36, 44 and 48 and FU Weeks 2 and 4:  $C_{trough}$
- On Day 84 (Week 12):  $C_{trough}$ ,  $t_{max}$ ,  $C_{max}$ ,  $C_{min}$ ,  $C_\tau$ ,  $AUC_\tau$ ,  $C_{avg}$ ,  $FI$ , Ratio  $CL/F^{\$}$ ,  $\lambda_z$ ,  $t_{1/2term}$ , Ratio  $C_{\tau,test/ref}^*$ , Ratio  $C_{max,test/ref}^{*\$}$ , and Ratio  $AUC_{\tau,test/ref}^{*\$}$

\* test = steady-state, and ref = Day 1 (to evaluate the accumulation index)

\\$ test = NA coadministered with JNJ-56136379, and ref = NAa

Other pharmacokinetic parameters may be estimated as appropriate for exploration of the data.

For the plasma pharmacokinetic parameters, definitions and methods of calculation are:

- $C_{max}$  maximum observed plasma concentration
- $C_{min}$  minimum observed plasma concentration
- $C_{trough}$  predose plasma concentration
- $C_\tau$  observed plasma concentration from time 0 to  $\tau$  hours postdose ( $\tau$  = treatment interval)
- $t_{max}$  time to reach  $C_{max}$
- $AUC_\tau$  AUC from time 0 to  $\tau$  hours postdose, calculated by linear-linear trapezoidal summation
- $AUC_{0-24h}$  AUC from time 0 to 24 hours postdose, calculated by linear-linear trapezoidal summation
- $AUC_{last}$  AUC from time 0 to the time of the last measurable (non-below quantification limit [BQL]) concentration, calculated by linear-linear trapezoidal summation

---

a This is not applicable to the monotherapy arms.

- $AUC_{\infty}$  AUC from time 0 to infinity, calculated as  $AUC_{last} + C_{last}/\lambda_z$ , where  $C_{last}$  is the last observed measurable (non-BQL) concentration; extrapolations of more than 20.00% of the total AUC are reported as approximations
- $C_{avg}$  average plasma concentration at steady-state over the treatment interval ( $\tau$ ) calculated by  $AUC_{\tau}/\tau$  at steady-state
- FI percentage fluctuation (variation between maximum and minimum concentration at steady-state), calculated as:  $100 \times ([C_{max} - C_{min}] / C_{avg})$
- CL/F total apparent oral clearance, calculated as dose/ $AUC_{\infty}$  after single dose, or as dose/ $AUC_{\tau}$  at steady-state
- $V_d/F$  apparent volume of distribution, calculated as dose/ ( $\lambda_z * AUC_{\infty}$ )
- $\lambda_z$  apparent terminal elimination rate constant, estimated by linear regression using the terminal log-linear phase of the log transformed concentration versus time curve
- $t_{1/2term}$  apparent terminal elimination half-life, calculated as  $0.693/\lambda_z$
- Ratio  $C_{max,test/ref}$  ratio of individual  $C_{max}$  values between test and reference
- Ratio  $AUC_{last,test/ref}$  ratio of individual  $AUC_{last}$  values between test and reference
- Ratio  $AUC_{\infty,test/ref}$  ratio of individual  $AUC_{\infty}$  values between test and reference
- Ratio  $C_{\tau,test/ref}$  ratio of individual  $C_{\tau}$  values between test and reference
- Ratio  $AUC_{\tau,test/ref}$  ratio of individual  $AUC_{\tau}$  values between test and reference

Dose-normalization will be done by dividing the relevant pharmacokinetic parameter by the dose (D).

Actual sampling times will be checked for major aberrations. Deviation of scheduled time points is allowed, however in case a major aberration occurs for an actual sampling time of >20.00% deviation from the scheduled time, or a sample is not taken on the scheduled day, this plasma concentration will be excluded from descriptive statistics in the plasma concentration table.

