- j. A subject diary will be provided to the subjects in the pharmacokinetic subgroup, and female subjects using hormonal contraceptives (regardless of type and route of administration). These subjects should report the times of study drug intake at home for 1 week prior to their Week 12 and Week 24 visits in this diary.
- k. Complete physical examination, including height, body weight, temperature, skin examination, and other body systems.
- l. Symptom-directed physical examination, including body weight and temperature.
- m. Vital signs include supine systolic blood pressure (SBP), diastolic blood pressure (DBP), and pulse rate.
- n. If blood sampling or vital signs measurement is scheduled for the same time point as ECG recording, the procedures should preferably be performed in the following order: ECG(s), vital signs, blood draw.

- o. Biochemistry samples must be taken fasted for at least 10 hours for measurement of phosphorus, calcium, creatinine clearance, and lipids. Subjects should bring their study drug with them to each visit and have that day's intake at the site.
- p. Creatinine clearance (estimated by the estimated Glomerular Filtration Rate [eGFR], which is calculated by the Modification of Diet in Renal Disease [MDRD] formula) will be assessed.
- q. In case of a positive dipstick result, a urine sample will be set aside for additional examination of the positive parameter (eg, quantification as applicable).
- r. Only applicable to subjects in the pharmacokinetic subgroup and subjects enrolled at a site with an on-site Fibroscan device.
- s. Sequencing on Day 1 (predose) will be performed by default if HBV DNA levels are within the ranges required for the sequencing assay; other samples may be sequenced based on the sponsor virologist's request.
- t. In virologically suppressed subjects, available historical data on HBeAg status before start of NA treatment will be collected in the eCRF.
- u. Quantitative HBeAg assessment will only be performed in subjects who are defined HBeAg-positive at screening based on a qualitative HBeAg assay.
- v. Exploratory serology samples may be analyzed at the sponsor's discretion. Samples may be used to assess virologic or serologic markers of HBV.
- w. Sparse pharmacokinetic sampling will be performed for all subjects. One sample predose at all indicated time points (except on Day 1: one sample 2 hours postdose only). Study drug should be taken on site. The time of study drug intake will be recorded.

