- x. Approximately 35% of all subjects (at selected sites only) will undergo semi-rich pharmacokinetic sampling (pharmacokinetic subgroup) predose and 2, 4, 12, and 24 hours postdose. The study drug should be taken on site. The time of study drug intake will be recorded.
- y. Approximately 35% of all subjects (at selected sites only) will have 24-hour urine sampling (pharmacokinetic subgroup) during the intervals 0-2, 2-12, and 12-24 hours postdose. This sampling schedule will require an overnight stay on site.
- z. Applicable to Treatment Arms 4-5 and 9-10 only.
  - aa. Immune cell samples (peripheral blood mononuclear cells [PBMC]) may be collected (selected sites only).
  - bb. The pharmacogenomic (DNA) sample should preferably be collected at baseline. This sample is optional and will only be collected from subjects who consent separately to this component of the study.
  - cc. PRO assessments will be performed by subjects at sites where appropriate translations are available. Subjects will complete the 5-level EuroQol 5-Dimension (EQ-5D-5L), Hepatitis B Quality of Life Instrument (HBQOL), Medical Outcomes Study Cognitive Functioning Scale-Revised (MOS-CFS Cog-R), and Short Form 36 version 2 (SF-36v2) on an electronic device during the specified study visits. The PRO assessments are preferably to be completed immediately after dosing.
  - dd. For women on stable ( $\geq 3$  months) hormonal contraceptive treatment at screening, as well as women starting hormonal contraceptive treatment during the study, in which case the first blood sampling should occur at the next scheduled visit (note: all hormonal contraceptives, regardless of type and route of administration).
  - ee. All study visits are to be scheduled relative to the baseline visit date and are to occur at the end of Weeks 1, 2, 4, 8, 12, 16, 20, 24, 28, 32, 36, 40, 44 and 48. The visit window is  $\pm 2$  days of the protocol-specified date at Weeks 1-4,  $\pm 5$  days of the protocol-specified date through Week 48.
  - ff. Eligibility to enter the treatment extension phase will be determined at Week 20 and Week 24 of the initial 24-week treatment phase, ie, subjects must have completed the initial 24 weeks of treatment and must have achieved a virologic response by Week 20 (HBV DNA  $<200$  IU/mL of the HBV DNA assay) without experiencing any safety concerns precluding continued study drug treatment as determined by the investigator.

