### ***Human Pharmacokinetics and Product Metabolism***

The current population pharmacokinetic (popPK) model based on data in healthy subjects allows to make predictions on exposures at different doses in CHB-infected subjects.

In healthy subjects, JNJ-56136379 is rapidly absorbed from the oral tablets, with a median  $t_{max}$  ranging between 1.26 and 3 hours in fasting conditions, and around 4 hours in fed conditions.  $C_{max}$  increased proportionally between 25 and 500 mg, but was later (median  $t_{max}$  4 hours) and less than dose proportionally at the dose of 600 mg. The AUC from time 0 to infinity ( $AUC_{\infty}$ ) increased proportionally between 25 to 600 mg single doses, and was approximately 16% higher in Asians. A single dose of 150 mg in 5 non-Asian subjects in fed conditions increased  $AUC_{\infty}$  by approximately 27%. The mean apparent volume of distribution (Vd/F) after single dose was ranging between 151 and 194 L in study 56136379HPB1001 and between 119 and 137 L in 56136379HPB1003 (Japanese subjects). JNJ-56136379 has a low systemic clearance, with total apparent oral clearance (CL/F) values ranging from 1.28 L/h and 1.41 L/h in study 56136379HPB1001 and from 0.852 to 1.03 L/h in study 56136379HPB1003. Mean terminal half-life ( $t_{1/2term}$ ) was comparable between studies 56136379HPB1001 and 56136379HPB1003, ranging between 93.3 and 116 hours across the dose levels in both studies, suggesting no significant difference in clearance between Asian and non-Asian subjects. In study 56136379HPB1003, approximately 18% of the administered dose was excreted via the kidney, resulting in a mean renal clearance of 0.161 L/h. This was comparable to what was observed in study 56136379HPB1001 Part 1.

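### The non-compartmental definitions in Protocol Section 9.4.3.1 do not fit the sampling: the NA interaction ratios have no within-subject NA-alone reference, and JNJ-56136379 Day 1 clearance and Week 12 half-life rest on 24 hours of data

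*Protocol*

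**What the plan says.** Section 2.1 of the Protocol makes the effect of JNJ-56136379 on NA pharmacokinetics a secondary objective. Section 1.2 plans no separate interaction study before Phase 2a. It relies on a population PK (popPK) assessment in this trial, with NA renal clearance in a subset.

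Section 9.4.3.1 lists the plasma parameters for JNJ-56136379 and/or NA:

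- Day 1 includes CL/F.
- Week 12 includes λz, terminal half-life and several ratios. Ratios marked with an asterisk compare steady state with Day 1 (accumulation). Those marked with a dollar sign (CL/F, Cmax, AUCτ) use "test = NA coadministered with JNJ-56136379, and ref = NA". A footnote excludes the monotherapy arms.
- The Cmax and AUCτ ratios are each defined as a "ratio of individual" values. The CL/F ratio has no definition of its own.
- CL/F is the "total apparent oral clearance, calculated as dose" over AUC∞ after a single dose and over AUCτ at steady state. λz is a log-linear regression on the terminal phase. For AUC∞, "extrapolations of more than 20.00% of the total AUC are reported as approximations".

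Under the Time and Events Schedule, about 35% of subjects "will undergo semi-rich pharmacokinetic sampling (pharmacokinetic subgroup) predose and 2, 4, 12, and 24 hours postdose", on Day 1 and at Week 12. The others give one predose sample per visit, "except on Day 1: one sample 2 hours postdose only". Section 1.1 reports a mean terminal half-life "ranging between 93.3 and 116 hours across the dose levels in both studies", and a median tmax of 1.26 to 3 h fasted "and around 4 hours in fed conditions".

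Section 9.4.1 says that JNJ-56136379 parameters will come from popPK modelling, optionally with Phase 1 data, and Section 11.4 repeats this. The SAP defers PK to a separate report (Section 1) and otherwise plans descriptive statistics, graphs and a listing (Section 9).

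**The concern.** An individual test/reference ratio needs both conditions in the same person. JNJ-56136379 is given from Day 1 in every active arm, so the NA-alone condition seems to be missing. An analyst who follows the definition literally must either leave the ratio empty or improvise a reference. Taking Day 1 would mix the interaction with NA accumulation in untreated subjects, and with first-dose JNJ-56136379 exposure in suppressed subjects.

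Separately, a drug with a half-life of about four to five days is to have a clearance to infinity and a terminal half-life computed from 24 h of samples. Section 9.4.1 assigns the same quantities to a different method. At stake are the definition of a secondary PK objective for which this trial is the planned check, and tabulated JNJ-56136379 values that could be badly wrong. The primary endpoint is not affected.

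**Working it through.** **The plan's own figures first.** Cavg = AUCτ/24: 88,101/24 = 3,671 (stated 3,670 ng/mL, 100 mg); 162,224/24 = 6,759 (stated 6,759, 170 mg); 83,161/24 = 3,465 (stated 3,465, 75 mg). Half-life as 0.693 × (Vd/F)/(CL/F) from the stated ranges is 74 to 105 h (study HPB1001) and 80 to 111 h (HPB1003), which overlaps the stated 93.3 to 116 h.

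**Who has an NA-alone profile?**

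- Arms 3 and 8 (untreated, combination): NA and JNJ-56136379 start together on Day 1, so neither profile is NA alone.
- Arms 5 and 10 (suppressed, combination): on stable NA for at least 12 months, but every Day 1 post-dose sample follows a JNJ-56136379 dose. Only the predose sample is free of it.
- Arms 1 and 6: excluded by the footnote.
- Follow-up: one sample per visit, no profile.
- Arms 2, 4, 7 and 9 (placebo+NA): NA alone at Week 12, but in different subjects.

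The individual ratio therefore has no reference. Day 1 exposure to JNJ-56136379 in Arms 5 and 10, as a share of steady state, is 1 − 2^(−24/t½) = 16% (93.3 h) to 13% (116 h) under one compartment, or 21 to 23% from the stated steady-state data below.

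**Day 1 CL/F of JNJ-56136379.** Share of AUC∞ beyond 24 h:

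- One compartment: 2^(−24/93.3) = 83.7%; 2^(−24/116) = 86.6%. With first-order absorption (tmax 1.26 to 4 h) and trapezoids at the planned times it is 84.3 to 87.2%.
- From stated steady-state data: Cmin = Cmax − FI × Cavg = 4,653 − 0.430 × 3,670 = 3,075 (100 mg) and 8,032 − 0.34 × 6,759 = 5,734 (170 mg). With linear kinetics, first-dose C24 = Cmin × (1 − 2^(−24/t½)) and single-dose AUC∞ = steady-state AUCτ. At 100 mg and 93.3 h: 3,075 × 0.1633 = 502; 502/(0.693/93.3) ≈ 67,600; 67,600/88,101 = 77%. The other three combinations give 78%, 78% and 79%.

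To keep extrapolation at 20% or less, the half-life would have to be at most 24 × ln 2/ln 5 = 10.3 h.

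**Week 12 λz and half-life of JNJ-56136379.** One-compartment fall = 1 − 2^(−Δt/t½): from 12 to 24 h, 8.5% to 6.9%; from 4 to 24 h, 13.8% to 11.3%. The stated data show a larger peak-to-trough fall: 1 − 3,075/4,653 = 34% and 1 − 5,734/8,032 = 29%. This points to an earlier, faster phase. Assuming 20 h from peak to trough, a log-linear fit gives 20 × ln 2/ln(4,653/3,075) = 33 h and 20 × ln 2/ln(8,032/5,734) = 41 h.

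Precision, with an assumed residual CV of 5 to 15% (not in the documents): for a slope on 4, 12 and 24 h, Sxx = 202.7 and SE = CV/√202.7. The relative SE is 47 to 176%, and the chance of a zero or positive slope is 2 to 29%.

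**The case against.** The strongest reply is that the protocol already plans a suitable method. Sections 3.1, 9.4.1 and 11.4 put PK on a popPK model, which needs neither a 24 h extrapolation nor a within-interval slope. Section 1.2 names popPK and renal clearance for the effect on NA. The separate popPK plan and PK/PD report are not available here. This stands, and it rules out three stronger readings that a reader might draw.

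- *That these parameters cannot be obtained at all.* PopPK can give JNJ-56136379 clearance and half-life, and the placebo+NA arms allow an NA comparison between groups. What fails is the stated formulas.
- *That the dollar ratio is a Day 1 to Week 12 ratio, or that Day 1 and Week 12 clearance are to be compared.* Day 1 is the reference only for the asterisk ratios, and the CL/F ratio does not carry the asterisk.
- *That the protocol breaks its own 20% limit.* The 20% is a labelling rule: larger extrapolations are reported as approximations. The label does not make a value that is about four-fifths extrapolated informative.

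It is also fair to say that the half-life evidence covers JNJ-56136379 only. The documents give no NA half-life, and NA CL/F on Day 1 in suppressed subjects is sound as dose/AUCτ.

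The reply does not remove the defect. Sections 9.4.1 and 11.4 assign popPK parameter derivation to JNJ-56136379. Section 1.2 states an intention for NA without naming a reference group or contrast. Section 11.4 and SAP Section 9 add descriptive statistics and displays. Section 9.4.3.1 still says that the listed parameters will be derived by its own formulas.

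**Conclusion.** The point holds as a mismatch of definitions. The NA interaction ratios, as individual ratios against NA alone, have no reference in any JNJ+NA subject. This needs no numerical assumption. For JNJ-56136379 only, Day 1 CL/F would be about 77 to 87% extrapolated. A Week 12 half-life from 24 h would be very imprecise if fitted to the late samples, or biased to roughly 33 to 41 h if fitted from the peak. These figures rest on the stated 93.3 to 116 h half-life, linear kinetics, mean values for Cmax, Cavg and fluctuation, and 20 h from peak to trough. The range of 77 to 87% spans the two models, and the conclusion is the same at either end. The remedy is wording. It deserves to be made because the interaction is a secondary objective.

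**What to change.** In Section 9.4.3.1 and the PK analysis plan:

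1. Define the dollar-marked comparison as the ratio of geometric means at Week 12, JNJ+NA versus placebo+NA, separately for ETV and TDF, with a confidence interval.
2. Support it with the Day 1 and Week 12 NA renal clearance already planned in Section 9.4.3.2, comparing Arms 5 and 10 with Arms 4 and 9. State that Day 1 in Arms 5 and 10 follows a first JNJ-56136379 dose and is only a near-reference.
3. For JNJ-56136379 only, remove non-compartmental Day 1 CL/F and Week 12 λz and half-life. Report CL/F as dose/AUCτ at Week 12 (the present Week 12 list has only its ratio). Take half-life from popPK, including the planned FU Week 2 and 4 samples, when about 8 to 13% and 1 to 2% of drug would remain (2^(−336/t½) and 2^(−672/t½)).
4. Keep the NA parameters, with Day 1 NA CL/F in suppressed subjects as dose/AUCτ.
5. Say which method, popPK or non-compartmental, governs each parameter.

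The cost is text, with no new samples. The price is precision: a between-arm ratio is wider than a within-subject one. If the 35% subgroup is spread evenly, it holds about 0.35 × 40 = 14 placebo+NA and 0.35 × 120 = 42 JNJ+NA subjects (21 per dose), before the split by ETV and TDF. The documents give no NA variability, so the interval width cannot be stated here.
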